## 7.2 LOST TO FOLLOW-UP

A participant will be considered lost to follow-up if: 1) he or she does not complete the end of month survey at the end of the 3-month (~90 day) home monitoring period **and** 2) study staff are unable to contact the participant after a minimum of 3 attempts.

The following actions must be taken if a participant fails to complete the end of the month survey at the end of the 3-month (~90 day) intervention period:

- The site will attempt to contact the participant and counsel the participant on the importance of completing the survey and ascertain if the participant wishes to and/or should continue in the study.
- The site will make every effort to regain contact with the participant (where possible, 3 telephone calls/emails/texts and, if necessary, a certified letter to the participant's last known mailing address or local equivalent methods) before a participant is deemed lost to follow-up. These contact attempts will be documented in the participant's study file.
- Participants that continue to be unreachable will be considered to have withdrawn from the study (with a primary reason recorded as lost to follow-up).

## 8 STUDY ASSESSMENTS AND PROCEDURES

### 8.1 ENDPOINT AND OTHER NON-SAFETY ASSESSMENTS

Participants will complete a baseline assessment, and daily and monthly assessments during a 3-month (~90 day) home monitoring period. Study data will be collected via self-report into web or app-based surveys and a consumer wearable (Fitbit®).

Eligibility and baseline procedures and assessments can be conducted virtually via teleconference/webinar. Daily, monthly and follow-up assessments will be conducted virtually through

the CareQOL app.

### **8.1.1 CONDITION (SCI, HD, HCT) DOCUMENTATION**

We will verify and document status of their condition (SCI, HD, HCT). Data must be obtained from official medical documentation (e.g. medical records).

### **8.1.2 CARE PARTNER ELIGIBILITY**

Confirmation of care partner eligibility according to criteria listed in Section 5, above, will be documented on the Eligibility CRF. It will occur prior to informed consent being obtained and before any study procedures associated with baseline assessment. Eligible individuals will then participate in the consent process, followed by randomization and baseline data collection.

### **8.1.3 DEMOGRAPHICS & CHARACTERIZATION**

All participants will complete a series of surveys designed to characterize the sample with respect to demographics, caregiving experiences, and usual coping or management strategies.

- Participant Demographics. A study-designed form will be used to capture demographic data including age, gender, race, ethnicity, education, marital status, work status, COVID history/status, care partner data, care recipient data, etc. Administration time for this assessment is ~5-10 minutes.
- Medical History, Medications, Treatments, COVID Questionnaire. Study designed forms will be used to capture medical history and current treatments/management strategies (medication and non-medication – e.g., exercise, mindfulness) and COVID history. Administration time for this assessment is 10 minutes.
- Caregiver Appraisal Scale (CAS). The CAS assesses positive and negative aspects of the caregiving role. Four separate subdomain scores (perceived burden, caregiver relationship satisfaction, caregiving ideology, and caregiving mastery) can be calculated; higher scores indicating better functioning. Administration time for this 47-item measure is ~5-10 minutes.
- United Huntington Disease Rating Scale (UHDRS) Independence Scale. The UHDRS Independence Scale is a single rating that the caregiver provides about the current level of the person that they care for's independence. Higher ratings indicate higher level of independence. Administration time is less than 1 minute.
- Supervision Rating Scale (SRS). This is a single rating that the caregiver provides about the overall amount of "supervision" that the person they care for receives. Ratings range from 1-13; higher ratings indicate greater levels of required supervision. Administration time is ~2 minutes.
- Care Recipient Medical Record Information. Study staff will complete a CRF with information about the person with SCI, HD or HCT for whom the care partner is providing care (e.g., date of diagnosis, details of diagnosis, disease stage/severity, etc.). This data will be entered into the study database by study staff.

### **8.1.4 FITBIT® AND CAREQOL APP**

Participants will be taught how to install both the Fitbit® and CareQOL apps onto their personal mobile devices. Participants will also be taught how to create and login to the necessary accounts. See section 6.2 for details regarding participant education.

- The study team will provide an access code for login to the CareQOL app.

- Participants will use a user id and personal email address of their choosing for their Fitbit® account.
- Data collected from the Fitbit® will be securely transmitted to the CareQOL app by user authentication token, which is comprised of a random series of characters that is used to securely query for user activity data.
- Participants will view their Fitbit® sleep and step-count data through the CareQOL app, though there are not restrictions on them also viewing the information in the Fitbit® app.

#### **8.1.4.1 FITBIT®**

All participants will don a wrist-worn Fitbit® with heart rate recording capabilities for the duration of the 10-day run-in period and 3-month (90 day) home monitoring period to monitor activity and sleep. While we intend to use the Fitbit Inspire HR®, we reserve the option to adopt a comparable device in the event of supply limitations or changes to the product line as long as there is minimal impact on the intervention delivery or primary outcome data integrity.

- Participants may use a personal Fitbit® if it has comparable features.
- Participants are expected to wear the Fitbit® continuously except for when charging and uploading data.
- Participants are expected to sync the Fitbit® daily.

#### **8.1.4.2 CAREQOL APP**

The study app (CareQOL) is the participant-facing platform for all daily, monthly and follow-up assessments, for viewing sleep and step count data from the Fitbit®, and for intervention delivery. The daily and monthly assessments, the link with the Fitbit®, and intervention delivery will cease after the home monitoring period has elapsed.

#### **8.1.4.3 RUN-IN HOME MONITORING PERIOD**

A 10-day run-in period will follow the baseline assessment. This period is to allow shipping time of the Fitbit® and provide the participant time to familiarize themselves with the study technology (Fitbit®, CareQOL app) and procedures. This period will also allow the study team to troubleshoot any potential barriers or issues that arise before the official start of the 3-month (90 day) home monitoring period. It also allows for data collection that can be used to inform the intervention messages once the home monitoring period begins.

#### **8.1.5 HRQOL ASSESSMENT**

Participants will complete a battery of HRQOL surveys; some will be administered daily and be used to drive the intervention, and others will be administered at baseline, monthly and during follow-up. The individual survey administration schedule is shown in the Table, and descriptions are provided below.

Table: HRQOL Assessment Schedule

	Baseline	Daily*	1m-	2m (30, 60d)	3m (90d)
Caregiver Strain SF	X		X	X	
Caregiver-Specific Anxiety SF	X		X	X	
Sleep-Related Impairment SF	X		X	X	
Fatigue SF	X		X	X	
Anxiety SF	X		X	X	
Depression SF	X		X	X	
Anger SF	X		X	X	
Self-Efficacy SF	X		X	X	
Positive Affect & Well-Being SF	X		X	X	
Perceived Stress	X		X	X	
Ability to Participate in Social Roles & Activities SF	X		X	X	
Global Health	X		X	X	
COVID HRQOL	X		X	X	
Single-item Caregiver Strain		X			
Single-item Anxiety		X			
Single-item Depression		X			
MedHistory/Medications/Treatment/COVID	X			X	
Adverse Event Status					X
Feasibility & Acceptability					X

- TBI-CareQOL Caregiver Strain Short Form (SF). TBI-CareQOL Caregiver Strain assesses perceived feelings of feeling overwhelmed, stressed and “beat-down” related to the care partner role. This measure is scored on a *T* metric ( $M = 50$ ;  $SD = 10$ ). Higher scores indicate more strain. The administration time for this measure is ~1 minute.
- TBI-CareQOL Caregiver-Specific Anxiety SF. TBI-CareQOL Caregiver-Specific Anxiety assesses perceived feelings of worry and anxiety specific to the safety, health, and future well-being of the person with TBI. This measure is scored on a *T* metric ( $M = 50$ ;  $SD = 10$ ). Higher scores indicate more anxiety. The administration time for this measure is ~1 minute.
- PROMIS Sleep-Related Impairment SF. PROMIS Sleep-Related Impairment evaluates the effect of poor sleep on daytime functioning. This measure is scored on a *T* metric ( $M = 50$ ;  $SD = 10$ ). Higher scores indicate more sleep-related impairment. Administration time for this measure is ~1 minute.
- PROMIS Fatigue SF. PROMIS Fatigue evaluates self-reported symptoms of fatigue, ranging from mild subjective feelings of tiredness to overwhelming exhaustion that may decrease one’s ability to perform activities of daily living. This measure is scored on a *T* metric ( $M =$

50; SD = 10). Higher scores indicate more fatigue. Administration time for this measure is ~1 minute.

- PROMIS Anxiety SF. PROMIS Anxiety assesses self-reported feelings of fear, anxiety and hyperarousal. This measure is scored on a  $T$  metric (M = 50; SD = 10). Higher scores indicate more anxiety. Administration time for this measure is ~1 minute.
- PROMIS Depression SF. PROMIS Depression assesses self-reported feelings of sadness and worthlessness. This measure is scored on a  $T$  metric (M = 50; SD = 10). Higher scores indicate more depression. Administration time for this measure is ~1 minute.
- PROMIS Anger SF. PROMIS Anger assesses self-reported feelings of irritability and frustration. This measure is scored on a  $T$  metric (M = 50; SD = 10). Higher scores indicate more anger. Administration time for this measure is ~1 minute.
- NIH Toolbox Self-Efficacy. NIH Toolbox Self-Efficacy assesses self-reported confidence in the ability to successfully perform specific tasks or behaviors related to one's overall functioning. This measure is scored on a  $T$  metric (M = 50; SD = 10). Higher scores indicate more self-efficacy. Administration time for this measure is ~1 minute.
- Neuro-QoL Positive Affect & Well-Being SF. Neuro-QoL Positive Affect and Well-Being assesses parts of an individual's life that are related to overall life meaning and purpose, well-being and satisfaction. This measure is scored on a  $T$  metric (M = 50; SD = 10). Higher scores indicate greater satisfaction. Administration time is ~1 minute.
- NIH Toolbox Perceived Stress SF. NIH Toolbox Perceived Stress is a self-report measure designed to assess an individual's feelings about the nature of events and individual coping resources. This measure is scored on a  $T$  metric (M = 50; SD = 10). Higher scores indicate more perceived stress. Administration time is ~1 minute.
- PROMIS Ability to Participate in Social Roles and Activities SF. PROMIS Ability to Participate in Social Roles and Activities assesses involvement in one's ability to participate in usual social roles and activities. This measure is scored on a  $T$  metric (M = 50; SD = 10). Higher scores indicate more ability to participate. Administration time is ~1 minute.
- PROMIS Global Health v1.2. This 10-item patient-reported outcome measure assesses overall physical, mental, and social health. This measure is scored on a  $T$  metric (M = 50; SD = 10); separate scores are generated for physical and mental health. Higher scores indicate better health. The administration time for this measure is ~3 minutes.
- COVID HRQOL. This 1-item patient-reported outcome measure asks how concerned the participant is about COVID-19 from 0 – 10. The administration time for this measure is less than 1 minute.

#### **8.1.5.1 BASELINE ASSESSMENTS**

Participants will be prompted by the CareQOL after registration to complete the baseline HRQOL assessments. Administration time is 10-15 minutes.

#### **8.1.5.2 DAILY ASSESSMENTS**

Participants will be prompted by the CareQOL app to complete a brief 3-item assessment once per day during the run-in and three-month (90 day) home monitoring periods. These questions will be answered directly on the app and involve <1 minute administration time in total. The daily assessments will include:

- TBI-CareQOL Caregiver Strain – single item assessment to evaluate self-reported caregiver strain. The individual items that are administered each day will vary.
- PROMIS Anxiety – single item assessment to evaluate self-reported anxiety. The individual items that are administered each day will vary.
- PROMIS Depression – single item assessment to evaluate self-reported depression. The individual items that are administered each day will vary.

### **8.1.5.3 MONTHLY ASSESSMENTS**

Participants will be prompted by the CareQOL app to complete a series of self-report surveys at the end of each month (day 30, 60, 90) during the 3-month (90 day) home monitoring period. They will also complete a post-intervention/app feasibility survey and retake the CAS (described above) at the end of month 3 (day 90). These surveys will be answered directly on the CareQOL app and/or by interview, and should take ~10-20 minutes to complete.

- Feasibility & Acceptability Questionnaire: At the 3-month (90 day) assessment only, participants will complete a Study Feasibility survey to assess the experience of the participant with the study methodology and technology, including the CareQOL app, Fitbit®, and the JITAI. Items are scaled from 1 to 5 to indicate level of agreement, where "1" indicates "strong disagreement" and "5" indicates "strong agreement." Administration time is 5 minutes.

Additionally, participants will update their medical history, medications, therapies, and COVID history and be queried about AEs at the end of month 3 (day 90).

- Medical History, Medications, Treatments, COVID Questionnaire. Participants will update their medical history and current treatments/management strategies (medication and non-medication – e.g., exercise, mindfulness) and COVID history. Administration time for this assessment is 10 minutes.
- Adverse Events. Participants will be asked about any changes in mental or physical health. Administration time is 5 minutes.

### **8.1.6 SEMI-STRUCTURED INTERVIEW (OPTIONAL: JITAI Group Only)**

Participants who have been randomized to the intervention group (JITAI) may be invited to complete an optional, in-depth semi-structured interview that will assess participant experiences and perceptions of the intervention messages that they received from the CareQOL app. The interview will be conducted via Zoom, audio-recorded and last for 45-60 minutes. Participants will be asked about their general experiences with the intervention messages they received while using the CareQOL app. Additionally, they will be shown specific messages from the CareQOL app and will be asked to provide their thoughts about these specific messages and their experiences with them. The interview will be completed after the 90-day study intervention period is completed (no more messages are being sent).

Participants who opt to complete this optional interview will be required to provide separate informed consent for this portion of the study, and participants will receive \$20 for completing the interview. The audio-recording of the interview will be transcribed and analyzed using qualitative analysis software (e.g., NVivo).

## 8.2 ADVERSE EVENTS AND SERIOUS ADVERSE EVENTS

### 8.2.1 DEFINITION OF ADVERSE EVENTS

The U-M IRBMED definition of an adverse event will be used for this study. The definition can be found at <https://az.research.umich.edu/medschool/glossary> and is below:

An adverse event (AE) is any experience or abnormal finding that has taken place during the course of a research project and was harmful to the subject participating in the research, or increased the risks of harm from the research, or had an unfavorable impact on the risk/benefit ratio. The event may or may not be caused by an intervention. Adverse events also include psychological, social, emotional or financial harms.

### 8.2.2 DEFINITION OF SERIOUS ADVERSE EVENTS

The U-M IRBMED definition of a serious adverse event (SAE) will be used for this study. The definition can be found at <https://az.research.umich.edu/medschool/glossary> and is below:

A serious adverse event (SAE) is any adverse experience occurring at any dose or level of participation that results in any of the following outcomes:

- Results in death,
- Is life-threatening,
- Requires inpatient hospitalization or prolongation of existing hospitalization,
- Results in persistent or significant disability/incapacity, or
- Is a congenital anomaly/birth defect.

### 8.2.3 CLASSIFICATION OF AN ADVERSE EVENT

#### 8.2.3.1 SEVERITY OF EVENT

All AEs will be assessed by a principal investigator(s), and/or if necessary, a study co-investigator.

The following guidelines will be used to describe severity.

- **Mild** – Events require minimal or no treatment and do not interfere with the participant's daily activities.
- **Moderate** – Events result in a low level of inconvenience or concern with the therapeutic measures. Moderate events may cause some interference with functioning.
- **Severe** – Events interrupt a participant's usual daily activity and may require systemic drug therapy or other treatment. Severe events are usually potentially life-threatening or incapacitating. Of note, the term "severe" does not necessarily equate to "serious".

#### 8.2.3.2 RELATIONSHIP TO STUDY INTERVENTION/EXPERIMENTAL MANIPULATION

All adverse events (AEs) will have their relationship to study procedures, including the intervention, assessed by an appropriately-trained investigator based on temporal relationship and his/her clinical judgment. All AEs will be categorized according to the likelihood that they are related or not related to the study intervention.

- **Related (Possible, Probable, Definite)**
  - The event is a known or suspected effect of the intervention or research procedures (e.g., listed in the protocol documents including, consent, publications, etc.)
  - There is at least a reasonable temporal relationship between the intervention or procedure and the event onset
  - The event abates when the intervention is discontinued
  - The event reappears upon a re-challenge with the intervention
  - The event includes data that was collected solely for research purposes
  - The event included disturbing or upsetting questions asked solely for research purposes
- **Not Related (Unlikely, Not Related)**
  - The event is NOT a known or suspected effect of the study intervention or procedures
  - The event is readily explained by characteristics of the study population
  - There is no temporal relationship between the intervention and event onset
  - An alternate etiology has been established

#### 8.2.3.3 EXPECTEDNESS

An investigator with appropriate expertise will be responsible for determining whether an adverse event (AE) is expected or unexpected. An event that is expected has been addressed or described in one or more of the following: Informed consent document for this study, IRB application for this study, grant application or study agreement, protocol or procedures for this study, published literature, other documentation, or characteristics of a study population. An AE will be considered unexpected if the nature, severity, or frequency of the event is not consistent with the risk information described.

#### 8.2.4 TIME PERIOD AND FREQUENCY FOR EVENT ASSESSMENT AND FOLLOW-UP

The occurrence of an AE or SAE may come to the attention of the study team via spontaneous report or formal assessment during month 3 of the 3-month home monitoring period, where participants will be asked to describe any physical or mental health worries/concerns since they began participating in the study. Regardless of the reporting mechanism, the study team will probe any concerns to get additional information and determine if it is an adverse event. Details will be documented in the participant study record.

Any side effects that are determined to be adverse events related to study participation will be documented on the study adverse event form in the study REDCap database and followed until resolution.

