## 2.3 RISK/BENEFIT ASSESSMENT

### 2.3.1 KNOWN POTENTIAL RISKS

The risks associated with the proposed study are minor and infrequent and include risks to: i) confidentiality; ii) frustration, stress and/or anxiety; iii) and skin irritation:

- i. **Confidentiality.** Confidentiality is a concern in this study. Every possible effort will be made to keep the research information in the strictest confidence, but we cannot absolutely guarantee that accidental disclosure will not happen. We remind participants that the responsibility of confidentiality rests with everyone: they should think carefully before discussing their role in this study with anyone since the effects of disclosure are unknown. Additionally, during the 3-month home monitoring period, participants may receive alerts when the participant is not in a private area. Participants will be informed that it is up to them where they complete the daily assessments, and if it is inconvenient/uncomfortable for them to complete the assessments when prompted they can wait and do it when it is more convenient/private or skip that assessment.

To reduce the risk to confidentiality, no personal identifying information will appear on or with the participant data, where possible. Each participant will be assigned a participant ID by the study team to maintain confidentiality. The participant's self-report data and CRF data will be identified with the participant ID. Additionally, an access code will be assigned

to each participant which they will use to enroll in the CareQOL app. Participants will register their study Fitbit® on the Fitbit® app using a username and email address of their choice. The study team will help the participant configure the Fitbit® app for minimal sharing; however, participants may opt to change those settings on their own (without study team knowledge). The data collected on the Fitbit® will be linked to the CareQOL app by user authentication token, which is comprised of a random series of characters that is used to securely query for user activity data; no identifying information (including email address or Fitbit® user ID) is saved in the CareQOL app.

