The study team will keep a master list of participant names and matching participant IDs. This master list will not be shared outside of the study team, and will be kept by site personnel in a password-protected file on a secure server or in a secure environment (e.g., locked cabinet, restricted access). No one other than the study team will have access to their master list. Informed consents will be stored in a study-specific database which contains only the informed consents and the informed consents will only be available to the study team members. The electronic data collection and storage systems used (e.g., CareQOL app, REDCap, Qualtrics, Fitbit®) are secure, web-based systems, with access to the study data limited to authorized individuals.

Lastly, the identities of all participants will be held in strict confidence to the extent provided by law. If findings from the study are published and/or presented at a professional meeting, no participant will be identified by name.

- ii. Fatigue, Frustration, Stress and/or Anxiety. It is possible that participants may experience fatigue, frustration or feel inconvenienced when completing the self-report surveys, when receiving the personalized interventions from the CareQOL app or from wearing the Fitbit®. Participants may also feel fatigue, stress and/or anxiety related to completing the study activities. Participants will be instructed that they can skip any questions that make them feel uncomfortable, and if they receive an app alert when it isn't convenient for them, they can wait and open the app when it is more convenient.
- iii. Skin Irritation. Some participants may get skin irritation from wearing the Fitbit®. Participants will be instructed to remove the device if this occurs and to contact the study team. Their band may be swapped out for a different type of wristband if they experience irritation. We offer a wide variety of wristbands to help make the Fitbit® as comfortable as possible.

To minimize the potential for risks, participants will be briefed in detail as to what they will experience throughout the study. All participants are informed that they may terminate participation from the study at any time without penalty.

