The JITAI aims to promote behavioral change through motivational messages that are delivered through the CareQOL app as push notifications. These notifications provide a trigger for participants to initiate or continue behavior change and/or monitor behaviors (through engagement with the app). The push notifications are low burden: participants can personalize the administration time (in a 5-hour window) and notifications can be viewed quickly on their phone's lock screen. Participants can also choose not to engage with the notification at the time it is sent if it is inconvenient – they can return to it later if needed.

The JITAI push notifications are aimed at promoting healthy behaviors (physical activity and good sleep hygiene) and improving mood (anxiety, depression, caregiver strain). If receiving a notification, the message will be randomly drawn from this pool of messages. Some messages will use participants' data directly in the messages (e.g., You walked an average of 8,120 steps this week), and most of messages will be personalized based on data (e.g., someone with low steps will get a different message than someone with medium steps than someone with high steps; high-medium-low). Messages are comprised of one or more of the following different types: 1) Data feedback; 2) Facts; 3) Tips; and 4) Support. Randomization of the days the participants receive messages and the message the participant receives from the pool will be done through the CareQOL app.

The study intervention period is 90 days (3 months); in addition, there is an ~10-day run-in period where participants will install/adjust/troubleshoot the study technology and the app will gather baseline data to use to tailor messages once the intervention period begins.

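### The one scheduled adverse-event query, as described, is limited to physical and mental health, so it does not solicit the social, financial and confidentiality harms that the protocol itself names

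*Combined protocol and SAP*

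**What the plan says.** Section 8.2.1 adopts the institution's broad definition of an adverse event and adds: "Adverse events also include psychological, social, emotional or financial harms". Section 2.3.1 groups the expected risks as "risks to: i) confidentiality; ii) frustration, stress and/or anxiety; iii) and skin irritation", describes them overall as small and rare, and gives one specific privacy example: "participants may receive alerts when the participant is not in a private area".

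The schedule of activities (1.3) and the assessment table in 8.1.5 mark adverse events only at the 3-month visit. The content of that query is described twice. Section 8.1.5.3 says: "Participants will be asked about any changes in mental or physical health". Section 8.2.4 says that "participants will be asked to describe any physical or mental health worries/concerns since they began participating in the study". Section 8.2.4 also allows events to surface by spontaneous report, and requires the team to probe any concern that is raised.

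**The concern.** The definition of what counts as harm is wider than the question used to find it. A participant whose only problem was that someone saw a study message, or that the study caused friction at home or an unwanted cost, could truthfully say that there was no change in health. Nothing would then be probed.

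Two later steps depend on what the query brings in. Section 8.2.3.3 treats an event as unexpected if, among other things, its frequency does not fit the risk information given. Section 8.2.5 reports only related events. For confidentiality, a frequency judgement would rest on unsolicited reports. The trial's purpose is to judge whether intensive monitoring is acceptable and to inform a larger study (9.2), so a near-empty row for privacy or social harm could be carried forward as reassurance that the data do not give.

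**Working it through.** No arithmetic applies: the plan gives no adverse-event rate, safety hypothesis or safety endpoint (sections 3 and 9.1). The check sets each harm that the protocol names against the query and against the other routes by which it might come to light.

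**Step 1. Harms named, and whether a physical or mental health question reaches them**

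| Harm | Named in | Within the day-90 query as described? |
|---|---|---|
| Psychological | 8.2.1 | Yes (mental health) |
| Emotional | 8.2.1 | Yes (mental health) |
| Social | 8.2.1 | No |
| Financial | 8.2.1 | No |
| Confidentiality | 2.3.1, risk i | No |
| Fatigue, frustration, stress, anxiety | 2.3.1, risk ii | Yes (physical or mental health) |
| Skin irritation | 2.3.1, risk iii | Yes (physical health) |

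Of the four harm types that the added sentence in 8.2.1 lists, two are outside the query. Of the three risk groups in 2.3.1, one is outside, and it is the one listed first.

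**Step 2. Whether another described procedure asks about the three that are outside**

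- *Spontaneous report with probing (8.2.4).* Probing starts once a concern has been raised. It does not raise one.
- *Staff contacts (5.5).* At least one in the run-in, one in the first week and one in each remaining month. They are listed as a retention measure, and no question about harm is specified.
- *Feasibility and acceptability questionnaire (8.1.5.3, 9.4.2).* Agreement items on experience with the study methods, app, Fitbit and JITAI. It is not described as asking about disclosure, relationships, work or cost.
- *Semi-structured interview (8.1.6).* Optional, JITAI arm only, and about the intervention messages.
- *Social roles measure (8.1.5).* A health-related quality-of-life outcome on ability to participate. It does not ask whether the study caused a social problem.
- *Unanticipated-problem rule (10.1.7).* Its criteria mention economic and social harm, but it governs reporting after something is known and puts no question to participants.

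None of these, as described, solicits social, financial or confidentiality harm.

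**Step 3. Whether exposure is plausible in both arms**

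Under section 6.1, both arms receive daily prompts on a personal device. The JITAI arm also receives messages, some of which use the participant's own data, and "notifications can be viewed quickly on their phone's lock screen". Exposure to unwanted disclosure is therefore possible in both arms and may differ between them, which is why a count by arm would be informative.

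**The case against.** The strongest reply is that the protocol describes its instruments only in outline. The adverse-event form, the feasibility items and the manual of procedures are not in the documents, and any of them might already ask about privacy or cost. That stands. It limits the point to what the protocol describes, and it means the two descriptions of the query should at least be brought into line with the definition.

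A reader might infer several stronger things that the documents do not support:

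- *That these harms can never be recorded.* They can, through spontaneous report, staff detection or the unanticipated-problem rule. They are unsolicited, not unreportable.
- *That study burden and device problems are also missed.* Section 2.3.1 does warn that "It is possible that participants may experience fatigue, frustration or feel inconvenienced when completing the self-report surveys", but fatigue and stress fall within a health question. Participants are told to contact the team about skin irritation, and the feasibility questionnaire addresses experience with the app, Fitbit and JITAI.
- *That the query is cut off from study procedures.* It covers the time since participation began, concerns are probed, and section 8.2.3.2 requires a judgement on relatedness to study procedures. A broad question followed by attribution is a legitimate design.
- *That messages are likely to expose participants to others.* The alert example in 2.3.1 concerns where daily assessments are completed, and participants may wait or skip. Staff help with alert and privacy settings (6.2), and the one example in 6.1 of a message using personal data is a step count. The documents give no rate of disclosure.

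**Conclusion.** The mismatch is real and minor. As described, the only scheduled query is narrower than the protocol's own definition and risk list in three respects: social harm, financial harm and confidentiality. If the query is asked as written, those three are likely to be under-counted. A low or zero count could not be cited to confirm that they are rare.

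This rests on two assumptions: that the adverse-event form follows the wording in 8.1.5.3 and 8.2.4, and that the feasibility items do not already ask about disclosure, relationships, work or cost. The size of any under-count cannot be stated from the documents. The primary, secondary and exploratory endpoints and the sample size are unaffected.

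**What to change.** First check the adverse-event form. If it already asks about these harms, correct the text of 8.1.5.3 and 8.2.4 to say so. If it does not, reconcile those two sections with 8.2.1 and 2.3.1 as follows:

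1. Keep the open question on physical and mental health.
2. Add short yes/no prompts to the day-90 query on (a) whether anyone saw study messages or data that the participant did not want them to see, and (b) whether the study caused relationship, work or cost problems.
3. Pass each yes to the existing probing, relatedness and expectedness steps.
4. Tabulate the answers by arm, with the number who answered as the denominator, and show prompted and spontaneous reports separately.

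The cost is a few items in an assessment already allotted 5 minutes, a minor amendment needing review board approval, and one table. Prompting will bring in more reports, most of them mild.
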